1.3 Pre-clinical rationale

DNA damaging agents (e.g. cisplatin and RT) are key treatments for many solid tumours including oesophageal cancer. Tumours can be resistant to current DNA-damaging based therapies due to the existence of an effective DNA Damage Response (DDR). The DDR consists of a series of molecular events that allow repair of damaged DNA and promote cell survival. ATM (Ataxia Telangiectasia Mutated) and ATR (ATM-and Rad3-related), members of phosphoinositol3-kinase like kinase family (PIKKs), are key components of the DDR. During normal DNA replication, ATR is recruited to stalled replication forks (replication stress) that can progress to DNA double strand breaks if unprotected. The recruitment and activation of ATR leads to cell cycle arrest in S phase whilst DNA is repaired; otherwise nuclear fragmentation occurs and apoptosis is initiated. Therefore, blocking ATR in an environment where replication stress is elevated as a result of treatment with radiotherapy or chemotherapy should improve killing of cancer cells. Consistently, it has been demonstrated that radiation and Cisplatin are more efficacious in tumour cells where kinase dead ATR has been expressed (1, 2).

M6620 (Berzosertib) is a potent inhibitor of ATR (inhibition constant K_i <300 pM) that blocks ATR activity in cells, with a concentration resulting in 50% maximal inhibition (IC_{50}) of 20 nM. ATR inhibition enhances the cytotoxic effect of DNA damaging drugs and IR in many cancer cell lines and primary human tumors. In contrast, normal cells tolerate ATR inhibition since they can activate compensatory DDR signalling via the ATM pathway. In xenograft models, M6620 (Berzosertib) markedly enhances the anticancer activity of numerous DNA damaging drugs and IR, often substantially delaying or completely halting tumor progression and promoting tumor regression. Dose range finding studies in mice (with gemcitabine and cisplatin) showed that maximal activity was observed when M6620 (Berzosertib) was administered intravenously at a dose of 20 mg/kg/week, given as a single dose or as two 10-mg/kg doses 3 days apart. Dose-responsive biomarker effects, which correlate with efficacy, support ATR inhibition as the primary mechanism of action.¹

Consistent with the compensatory role the ATM/p53 pathway plays in response to ATR inhibition in normal cells, defects in this pathway result in increased cell sensitivity to ATR inhibition. In isogenic cell studies it has been shown that loss of ATM itself or one of its principle substrates, p53, can markedly increase cell sensitivity to ATR inhibition. Similarly, in a large panel of 119 genetically-diverse cancer cell lines, *TP53* mutational status was shown to correlate with response to ATR inhibition in combination with DNA damaging agents.

Pires *et al* (10) showed that VE-821 also inhibited ATR-mediated signalling in response to the replication arrest induced by severe hypoxia and that ATR inhibition consistently sensitised tumour cell lines to radiation across a range of oxygen tensions. In addition, it was shown for the first time that treatment with the ATR inhibitor led to a decrease in HIF-1-mediated signalling, suggesting that it could also inhibit the biological consequences of tumour hypoxia such as increased invasion, metastasis and angiogenesis.

Fokas *et al* (11) demonstrated radio-sensitisation and chemosensitisation to gemcitabine using the ATR inhibitor VE-822 in p53 and KRAS mutant pancreatic ductal adenocarcinoma (PDAC) *in vitro* and *in vivo* (VE-822 is another pre-clinical ATR inhibitor chemically identical to M6620 (Berzosertib)). The selectivity of VE-822 was initially demonstrated through selective reduction in CHK1 phosphorylation without inhibition of ATM or DNA-PK signalling pathways. In xenograft experiments, the activity was profound, to the extent that the combination of RT with VE-822 prevented MiaPaCa-2 tumour regrowth in some mice. Importantly, VE-822 did not increase normal cell radiosensitivity and chemosensitivity *in vitro*, similar to the VE-821 studies described previously.

ATR inhibition has not been previously tested specifically on oesophageal cancer cell lines or xenografts. We have recently demonstrated chemosensitisation (cisplatin) and radiosensitisation of ACA and SCC cell lines using VE-822. These data show that the addition of the ATR inhibitor (VE-822) increases sensitivity to radiation as well as cisplatin in 3 oesophageal cell lines (OE21, FLO-1 and OE33) both under normoxic and hypoxic conditions (<0.1% O₂) ([name], unpublished data).

1.4 Clinical rationale

There is strong scientific rationale for combining ATR inhibitors with DNA damaging agents such as radiation and cisplatin. In particular, ATR inhibition has been shown to be cytotoxic to tumour cells with an impaired DNA damage response (DDR), such as those with deficiency in the ATM- or p53 pathway [7]. The high incidence of p53 mutations (~89.9% in SCC of the oesophagus and ~72% in ACA) [8, 9] and the fact that cisplatin and radiation are key therapeutics, makes oesophageal cancer an attractive tumour type to test the activity of an ATR inhibitor [8-10]. Given the reported synthetic lethal relationship between ATM and ATR, it is likely that ATR inhibition in

an ATM- or p53- deficient background will offer a specific and effective way of targeting OAC and SCC of the oesophagus, and enhance the current standard of care.

The in vitro and in vivo studies mentioned above, have shown that M6620 (Berzosertib) can enhance sensitivity of cancer cells to chemotherapy and radiotherapy without enhancing radiosensitivity in normal tissue [7, 11]. This tumour selectivity suggests there will be little or no enhancement of radiation toxicity and therefore, is likely to allow delivery of full doses of chemotherapy and radiotherapy. In contrast, recently reported studies in gastro-oesophageal cancer, toxicity due to addition of novel agents resulted in reduction of dose intensity of standard treatment and inferior survival in the experimental arms[1, 12] underlining the importance of this lack of toxicity in normal tissues.

In an ongoing study (VX12-970-001), M6620 (Berzosertib) is being dosed in combination gemcitabine and in combination with cisplatin to determine the MTD of M6620 (Berzosertib) in combination with these agents. To date, 140 mg/m² of M6620 (Berzosertib) in combination with 75 mg/m² of cisplatin was tolerated. Also, 210 mg/m² of M6620 (Berzosertib) in combination with 1000 mg/m² of gemcitabine was tolerated and is the recommended phase II dose. In another ongoing study (VX13-970-002), M6620 (Berzosertib) at 90 mg/m² in combination with AUC 5 of carboplatin was tolerated. Also, evaluation of on-target tumor biopsies at these doses demonstrated target engagement as measured by ATR-mediated phosphorylation of Chk1 (P-Chk1).

The trial will be divided into 2 stages, stage A and Stage B. Stage A will consist of 2 parts, part A1 will explore the combination of M6620 (Berzosertib) plus radiotherapy and Stage A2 will explore the combination of M6620 (Berzosertib) plus chemotherapy in the palliative setting. Stage B, will explore the combination of all 3, M6620 (Berzosertib) plus chemoradiotherapy in the radical setting. In Stage A1 of the study M6620 (Berzosertib) will be combined with radiotherapy for the first time and the starting dose will be 140mg/m² M6620 (Berzosertib), which has been well-tolerated. Intravenous (IV) administration was shown to be better tolerated than oral administration in dogs and will be used in the study. We have chosen to administer M6620 (Berzosertib) with daily palliative radiotherapy in Stage A1 to study specific interaction of M6620 (Berzosertib) with radiotherapy which is the DNA damaging agent at this stage. In Stage A2 of the study M6620 (Berzosertib) will be combined with Cisplatin and Capecitabine combination chemotherapy for the first time and the starting dose will be 90mg/m² M6620 (Berzosertib). We have chosen to administer M6620 (Berzosertib) after chemotherapy to explore possible additional interactions with cisplatin which binds with DNA to form intrastrand crosslinks and adducts that cause changes in the conformation of the DNA and affects DNA replication fluoropyrimidines whose primary mechanism of action is the inhibition of thymidylate synthase. Stage A1 and A2 will give an indication of toxicity profile before administration with radiotherapy, Capecitabine and Cisplatin during chemoradiotherapy. Data from the VERTEX study VX12-970-001 indicates maximum benefit from the chemotherapy and M6620 (Berzosertib) treatment combination comes with administration of M6620 (Berzosertib) between 14 and 36 hours post administration of DNA damaging agent (VERTEX, unpublished results). Therefore we propose to administer M6620 (Berzosertib) 24 hours post cisplatin infusion.

2 TRIAL DESIGN

This will be a single arm, open-label, phase I dose escalation trial using the Time-To-Event Continual Reassessment Method (TiTE-CRM) to find the optimal treatment schedule. The TiTE-CRM method uses critical toxicity summaries of accumulated patient data from all participants treated with at least one dose of the IMP within the corresponding trial stage and for whom up-to-date data has been provided (trial unit will endeavour to ensure contemporaneous data is received for all participants) and it is not necessary for a patient to complete the full observation period before consenting the next patient. This results in a better estimation of the MTD and shorter study duration respectively and is particularly useful in trials involving radiotherapy where the toxicity follow-up phase is longer.

The trial design ensures no treatment schedule skipping and the treatment schedule assigned will be that estimated to be closest to but not above the MTD. However, if the lowest schedule is estimated to be above the MTD we will keep assigning the lowest schedule until we are certain it is too toxic, at which point the trial may start again using a lower dose of drug. When escalating, the treatment schedule cannot skip an untried dose but there will be no restriction on treatment schedule de-escalation. Each escalation decision will be made by the TMG based on the recommendation from the TiTE-CRM model and the accumulated experience of the

recommended schedule. If the TMG is unable to reach a decision or a stopping rule has been met the Safety Review Committee (SRC) will meet.

The trial consists of three stages A1, A2 and B which are described in the following sections. Stages A1 and A2 will run concurrently and will inform the starting dose of M6620 (Berzosertib) for Stage B.

2.1 Stage A1

The aim is to find the M6620 (Berzosertib) treatment schedule when combined with radiotherapy that is associated with no more than 25% dose limiting toxicity rate on the basis that palliative oesophageal radiotherapy is associated with approximately 15-20% grade 3/4 toxicity. Six treatment schedules are proposed. Each schedule comprises a specific combination of dose and dosing frequency. There are two possible M6620 (Berzosertib) doses and three dosing frequencies (see section 8.1). The radiation dose remains consistent across all treatment schedules.

The treatment involves 3 weeks of daily radiotherapy and M6620 (Berzosertib) at a pre-determined frequency dependent on the treatment schedule allocated to the individual patient. The follow-up of a further 6 weeks provides a DLT observation window of a total of 9 weeks. An initial cohort of three patients will receive the starting schedule (lowest dosing frequency) at the starting dose, 140mg/m². The fourth patient will not be recruited until all three patients have been followed for the minimum of 9 weeks from the start of radiotherapy or the occurrence of a DLT.

Subsequently, all eligible patients will be continuously recruited and the TiTE-CRM will be used to assign their treatment schedule. To ensure enough information is accumulated to inform the assignment of the treatment schedule to the subsequent patient, recruitment will be managed through allocation of treatment slots (see section 4.4 for further details).

2.1.1. Stage A1 stopping rules

Stage A1 will pause for safety if, at any point in the trial, there is sufficient evidence to suggest that schedule 1 is too toxic. More specifically, we will consider schedule 1 to be too toxic if, given all the available data, there is a high probability that the DLT rate is greater than the target toxicity level of 0.25. If all 3 patients in the first cohort have DLTs then schedule 1 is too toxic and the trial will be re-started. At this point, three extra schedules will be introduced at 90mg/m² and varying dosing frequencies, namely (schedule -3, -2 and -1). Once the trial is restarted, the lowest schedule, schedule -3, will be explored first. There will then be 9 treatment schedules to explore (the original 6 plus the 3 dosing frequencies at the lower dose). If the first 3 patients recruited to schedule -3 experience DLTs then the trial will stop. If schedule 1 is found to be too toxic later in the trial when more than 3 patients have been recruited, a SRC meeting will be convened to decide whether the trial should be restarted using the lower dose of 90mg/m².

Stage A1 will stop for success when either a total of 10 patients have been assigned to a particular treatment schedule or 20 patients have been recruited, whichever occurs first. When 10 patients in Stage A1 have been assigned to a particular treatment schedule, recruitment will be paused until there are no more than three patients without full follow-up (either DLT or 6 weeks after the end of treatment), i.e. until there is full follow-up information on at least seven patients. If the MTD changes, recruitment may start again.

Based on simulations and assuming a patient will be recruited every 8 weeks, the average number of patients required for Stage A1 is 18, which we aim to recruit in 24 months.

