3.2 Dose allocation

The trial design ensures no treatment schedule skipping and the treatment schedule assigned will be that estimated to be closest to but not above the target toxicity level (TTL). However, if the lowest schedule is estimated to be above the TTL we will keep assigning the lowest schedule until we are certain it is too toxic, at which point the trial may start again using a lower dose of drug. When escalating, the treatment schedule can only increment by one level if escalating to an untried schedule, but there will be no restriction on treatment schedule de-escalation. Each escalation decision will be made by the TMG based on the recommendation from the TiTE-CRM model and the accumulated experience of the recommended schedule. Full details of each dose decision are found in the Protocol Decision Point Plan (V1.0, 28Jun2019) but briefly: TMG to review the dose selected by the statistical model on the basis of the accumulated data and either:

- Confirm the selected dose **or**
- Over-rule the selected dose and choose an alternative dose for the next participant & may convene a meeting of the Safety Review Committee (SRC) **or**
- Agree to convene a meeting of the Safety Review Committee (SRC) for further input as the TMG is unable to reach a decision **or**

Agree that a protocol defined stopping rule has been met and that the trial should be stopped.

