3.3 Stopping rules for toxicity

The same stopping rule for safety applies to all 3 stages of the study: each stage will stop for safety if, at any point in the stage, there is sufficient evidence to suggest that the lowest treatment schedule is too toxic. Specifically, within a particular stage, the lowest schedule will be considered too toxic if, given all the available data, there is a high probability that the DLT rate is greater than the target toxicity level for that stage, i.e. if $P(\text{Toxicity at treatment lowest schedule} > \text{TTL} | \text{data}) > 0.95$.

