3.4 Summary of trial design for all stages

The table summarises the design features of the design for stages A1 and A2, and Figure 1 shows the flow of patients through the trial.

Table 1: Design features for all stages of the study

Assumptions	A1	A2	B**
Target toxicity level	0.25	0.30	
Maximum number of subjects	20	20	
Number of treatment schedules	6	4	
Stopping rules	10 on a schedule	6 on schedule 4	
Toxicity stopping rules	$P(\text{Toxicity at treatment schedule 1} > \text{TTL} \text{data}) > 0.95$		
Definition of MTD	Treatment schedule that is closest to but not above the TTL		
Dose escalation rules	No dose skipping when escalating, no restrictions on de-escalation		
Dose toxicity curve	Power curve with prior $N(0, 1.158^2)$		
DLT window	9 weeks	4 weeks	

A phase I dose escalation safety study combining the ATR inhibitor VX-970 with chemoradiotherapy in oesophageal cancer using time to event continual reassessment method (funded by CRUK and Merck)

EudraCT Number: 2015-003965-27

[figure not shown]
Number in first cohort*	3	3
Skeleton	0.12	0.17
	0.15	0.20
	0.18	0.25
	0.20	0.30
	0.22	
	0.25	

* This is the number assigned the first treatment schedule

** Design features for Stage B omitted for this version of the SAP.

A phase I dose escalation safety study combining the ATR inhibitor VX-970 with chemoradiotherapy in oesophageal cancer using time to event continual reassessment method (funded by CRUK and Merck)
 EudraCT Number: 2015-003965-27

Figure 2: Trial Flow Chart

A phase I dose escalation safety study combining the ATR inhibitor VX-970 with chemoradiotherapy in oesophageal cancer using time to event continual reassessment method (funded by CRUK and Merck)
EudraCT Number: 2015-003965-27

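### Stage A1 can stop for success with ten patients on the lowest schedule while the model puts every schedule above the 25% DLT target, and no rule links that case to the restart review

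*Protocol*

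**What the plan says.** Four rules meet here.

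- **Success stop.** Protocol 2.1.1: "Stage A1 will stop for success when either a total of 10 patients have been assigned to a particular treatment schedule", or 20 recruited if that comes first. The Stage A1 stopping rules in the SAP repeat this, and SAP Table 1 shortens it to "10 on a schedule". None of the three mentions the estimated DLT rate. At ten, recruitment pauses until no more than three patients lack full follow-up, and may resume if the MTD changes.
- **Assignment when nothing qualifies.** Protocol section 2: "if the lowest schedule is estimated to be above the MTD we will keep assigning the lowest schedule until we are certain" that it is too toxic. SAP 3.2 has the same rule, written against the target toxicity level (TTL).
- **Safety stop.** SAP 3.3 requires that "there is a high probability that the DLT rate is greater than the target toxicity level for that stage", and sets the threshold at a posterior probability above 0.95. Outside the first cohort, the 90 mg/m² restart in Protocol 2.1.1 is put to the SRC only once schedule 1 has been found too toxic.
- **What the stage is for.** The primary endpoint (Protocol 3.1.1) is the highest schedule with a DLT rate under 25%. SAP Table 1 defines the MTD as "Treatment schedule that is closest to but not above the TTL".

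**The concern.** Counting ten assignments is a reasonable sign of convergence when the model chose the schedule because it was at or below target. The lowest schedule is different. It is also assigned by default, when the model finds no schedule at or below target. Those default assignments count towards ten in the same way.

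There is therefore a band, from an estimate above 0.25 up to a probability of 0.95, in which patients accumulate on schedule 1 and the tenth triggers the success stop. The other provisions miss this case:

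- The pause clause reopens recruitment only if the MTD changes, and here the assigned schedule was and remains schedule 1.
- The restart review needs a finding of too toxic, which has not been made.

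The stage would close as a success in a situation close to the one the lower-dose schedules were written for, with no instruction to consider them.

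**Working it through.** **Inputs** (SAP 3.1.1, 3.3 and Table 1): g_k = d_k^exp(α); α ~ N(0, 1.158²); Stage A1 skeleton 0.12, 0.15, 0.18, 0.20, 0.22, 0.25; TTL 0.25; safety threshold 0.95; first cohort of 3; no skipping of untried schedules; maximum 20. A patient with a DLT has weight 1; a patient without has w = ½(u/T + v/D).

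**Reproducing the plan's own figure.** The documents give 18 patients (10, 20) for Stage A1. Simulating these rules with one patient every 8 weeks, true rates equal to the skeleton and DLT times uniform over 9 weeks (the last two are assumptions) gives a mean of 17.3 (10, 20). That is close enough to rely on the implementation.

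**Ten patients on schedule 1, all followed fully.** With k DLTs the posterior for α is proportional to exp(−α²/(2 × 1.158²)) × g^k × (1 − g)^(10−k), where g = 0.12^exp(α). The event g > 0.25 is α < ln(ln 0.25 / ln 0.12) = ln(1.386/2.120) = −0.425. Numerical integration gives:

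| DLTs in 10 | Estimate, schedule 1 | P(rate > 0.25) | Result under the rules |
|---|---|---|---|
| 2 | 0.215 | 0.34 | success, schedule 1 qualifies |
| 3 | 0.301 | 0.62 | success, none qualifies |
| 4 | 0.384 | 0.83 | success, none qualifies |
| 5 | 0.466 | 0.944 | success, none qualifies |
| 6 | 0.546 | 0.986 | safety stop |

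The model is monotone, so when schedule 1 is above 0.25 all six schedules are.

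**Weights at 5 in 10.** Each DLT-free patient contributes (1 − w·g). One such patient at w = 0.8, the rest at 1, gives P = 0.951; two at 0.9 also give 0.951. Either crosses 0.95. For 4 in 10, three DLT-free patients at 0.8 give 0.87, so that row stands.

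**Is the state reachable?** Take DLTs in patients 1, 5 and 9, with full follow-up at each decision. The schedule 1 estimates after patients 3 to 10 are 0.314, 0.262, 0.370, 0.325, 0.288, 0.259, 0.328 and 0.301. All exceed 0.25, so each next patient goes to schedule 1. The largest P along the path is 0.73, so the safety rule never fires.

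**How often?** Share of stages that stop for success with schedule 1 estimated above 0.25. Column A uses staggered follow-up, the SAP weights and true rates rising 5 points per schedule (4,000 trials per row), except that the first row uses the skeleton. Column B counts only the route through ten on schedule 1, with higher schedules at +3, +6, +8, +10 and +13 points (4,000 trials; 2,000 for the 0.20 row).

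| True rate, schedule 1 | A: any success stop (through ten on schedule 1) | B |
|---|---|---|
| skeleton (0.12) | 10.6% (10.0%) | – |
| 0.20 | – | 29% (32% by any route) |
| 0.25 | 49.0% (45.3%) | – |
| 0.30 | 56.1% (52.7%) | 52% |
| 0.35 | 56.6% (53.8%) | 54% |
| 0.40 | 51.7% (49.9%) | 53% |
| 0.45 | – | 47% |
| 0.50 | 36.4% (35.9%) | – |

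At 0.40 in column A, 39.4% of stages stop for safety.

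**The case against.** The best defence is that the success stop ends recruitment and does not name an MTD. A reader might infer that schedule 1 would be carried forward as the recommended schedule. The documents do not support that: SAP 7.2.1 reports posterior probabilities with credible intervals, and the MTD definition in Table 1 would return no schedule. Protocol section 2 also has the SRC meet when a stopping rule is met, and SAP 3.2 lets the TMG over-rule the model. These points stand and limit the harm. They leave the outcome to discretion, though, because no text says what is declared when no schedule qualifies.

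A reader might also infer that the success label opens Stage B. It does not. The trigger in Protocol 2.3 counts ten recruited to A1 without a restart, whatever the label, and it only convenes the SRC.

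It is also tempting to say that any observed rate from 30% to 50% counts as success. At 5 in 10 that fails once follow-up or M6620 dosing is slightly incomplete. Nor does 3 in 10 show that schedule 1 is too toxic: P is only 0.62, and the 95% credible interval runs from about 0.09 to 0.57.

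Finally, true rates of 0.30 and above are pessimistic beside a skeleton value of 0.12, so the skeleton figure belongs next to them. The Protocol Decision Point Plan and the SAP's simulation appendix were not available and may address the case.

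**Conclusion.** The gap is real. As written, Stage A1 can be declared a success and closed to recruitment when its own model places no schedule at or below target, contrary to the primary endpoint. The result for 3 and 4 DLTs in 10 rests only on SAP inputs and full follow-up; 5 in 10 also needs all weights equal to 1. The frequencies (about 11% under the skeleton, about 30% at a true schedule 1 rate of 0.20, about 45-55% at 0.30-0.45) rest on assumed true rates, and those from the staggered runs also on uniform DLT times.

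The harm is limited to a wrong success declaration and closure without a rule that brings this case to the existing restart review. It does not extend to a wrong MTD or to the opening of Stage B.

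**What to change.** In Protocol 2.1.1, the SAP's Stage A1 stopping rules and SAP Table 1, let the 10-patient stop and the 20-patient cap count as success only if, after the pause follow-up, at least one tried schedule has a posterior DLT estimate at or below 0.25. Otherwise report that no schedule is currently estimated at or below target, with the posterior and credible interval. Refer the stage to the SRC to decide between continuing recruitment up to the existing cap of 20 and the existing restart provision. The wording should not say that schedule 1 is too toxic.

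The text change is a sentence or two in each place. Relabelling alone adds no patients: mean size under the skeleton stays at 17.3. The downside is that some stages in which schedule 1 is truly acceptable would go to SRC review instead of being called a success, about 11% under the skeleton and about 30% at a true rate of 0.20.

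Continuing to 20 reduces this. Under the skeleton the share ending with no qualifying schedule falls from 10.6% to 3.6%, for a mean of 17.8 patients. At a true rate of 0.35 it falls from 56.6% to 32.6%; safety stops rise from 27.8% to 41.8%, successes from 15.7% to 25.6%, and mean size from 10.9 to 14.2. The SRC should see both sides of that trade.
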